## **10.6. Preparing the Study Medication for Application**

To perform a study medication treatment for the identified common wart a staff member will select the appropriate study medication applicator from the identified subject's kit. The following instructions outline the procedure for application of the study medication to the identified common wart. During each in-office treatment visit, the Investigational Study Staff will be responsible for reviewing the following instructions with the subject/parent/legal guardian and ensure that they understand how to properly prepare the applicator and apply the A-101 study medication.

- For the in-office treatment applications, the Investigational Study Staff member will prepare the A-101 study medication applicator for all subjects, regardless of age by:
  - Washing their hands prior to, and after completing the study medication treatments
  - Wear nitrile or vinyl examination gloves during the treatment; **latex gloves are prohibited**
  - Visually inspect the applicator for damage:
    - If the applicator appears damaged do not use it for the treatment, contact the study monitor for disposal instructions and select an unused applicator with the next highest number for the treatment

If the applicator is intact, proceed with the applicator preparation process as outlined in [Figure 1](#).

**Figure 1: Diagram Showing the Process for Preparing A-101 Study Medication**

1. Each common wart should be cleaned using an alcohol wipe prior to application of A-101 45%.
2. Hold the applicator so that the applicator cap is pointing up.
3. Crush the ampule in the applicator by applying pressure to the center of the barrel of the applicator.
4. Remove the sleeve.
5. Tap the barrel of the applicator to ensure the solution is free of the crushed ampule.
6. Gently remove the cap by twisting while pulling away from the applicator.
7. Express a single drop of A-101 45% so that the tip of the applicator becomes wet.
8. Apply the solution to the identified warts in a circular motion.

All subjects will be supplied with treatment application instruction sheets at the completion of each in-office visit.

## **10.7. Applying Study Medication**

All subjects that are between the ages of 1 and 17 will have their A-101 study medication applied by a parent/legal guardian. Parents/legal guardians of children must ensure that the child does not put the treated area in their mouth, or eyes, until completely dry after the application. If the treated area is not completely dry 10 minutes after the application, the area should be blotted dry. For in-office visits, the subject's parent or legal guardian will apply the A-101 study medication in front of a member of the investigational study staff to ensure there is a clear understanding regarding how the study medication should be handled.

Subjects 18 years of age and older will apply their A-101 study medication to his/her identified common warts in the presence of the treating physician or member of the investigational staff during in-office visits. The second weekly application will be performed at home.

The following instructions will be used by all subjects/parents/legal guardians applying A-101 study medication to all identified common warts:

- Do not apply the study medications to eyes, nose, mouth, mucous membranes, or open wounds
- Wear nitrile or vinyl examination gloves during the treatment; **latex gloves are prohibited (All subjects will be supplied with nitrile or vinyl examination gloves to be used for at home applications)**
- Thoroughly cleanse the common wart by firmly rubbing with a swab/wipe wetted with 70% isopropyl alcohol
- Using firm pressure and with the tip of the applicator held over the wart, squeeze in the middle of the applicator to apply one drop of study medication onto the common wart. Using the smaller side of the applicator tip, move the applicator around in a circular motion to fully saturate the lesion. Apply the study medication for approximately 15 seconds.
- Minimize exposure to the surrounding normal skin
- During the treatment process remove excess study medication from the surrounding skin using a clean absorbent wipe.
- Ensure the identified common wart is fully saturated with study medication at the end of the ~15 second application
- Allow the treated wart to remain undisturbed for ~15 seconds
- After ~15 seconds repeat the ~15 second application process
- Repeat the application/waiting cycle until the study medication has been applied to each identified Wart up to 3 times.
- If severe erythema and edema develop, then the treatment cycle should be discontinued for that specific treatment application.
- Absorb any remaining A-101 study medication and dry the common wart and the surrounding skin without wiping or rubbing.

## **10.8. Dose Modification**

If a subject refuses to have a study medication treatment the investigator must report the visit number, visit date, and state the reason the subject refused to allow treatment in the subject's CRF.

If the subject's refusal is associated with an AE, the investigator must also report the event on the appropriate CRF.

## **10.9. Breaking the Blind**

The blind may be broken ONLY in the event of a medical emergency, in which knowledge of the study medication identity is critical to the management of the subject's course of treatment.

Before breaking the blind, the investigator should determine that the information is necessary. In many cases, particularly when the emergency is clearly not study medication-related, the problem may be effectively managed by assuming that the subject is receiving an active study medication without the need for unblinding.

If deemed necessary to break the blind for a study subject, attempt to contact the Medical Monitor to obtain permission to break the blind of a particular subject. If it is not possible to contact the Medical Monitor beforehand, contact her/him as soon as possible after breaking the blind for a subject.

## 11. PREVIOUS AND CONCOMITANT THERAPIES

### 11.1. Previous Therapy

During Visit 1, the investigator or designee will question the subject to ensure they have not used any excluded therapies within the specified period prior to Visit 2 to the identified common warts:

- Intralesional Therapy
  - Immunotherapy (*e.g.*, *Candida* antigen, mumps antigen, *Trichophyton* antigen); 8 weeks
  - Anti-metabolite therapy (*e.g.*, bleomycin, 5-fluorouracil); 8 weeks
- Systemic Therapy
  - Immunomodulatory/immunosuppressant therapy (*e.g.*, etanercept, alefacept, infliximab); 16 weeks
  - Glucocortico-steroids (inhaled and intra-nasal steroids are permitted); 28 days
- Topical Therapy
  - LASER (*e.g.*, pulsed-dye laser [PDL], light (*e.g.*, intense pulsed light [IPL], photodynamic therapy [PDT], other energy-based therapy); 6 months
  - Immuno-therapy (*e.g.*, imiquimod, squaric acid dibutyl ester [SADBE], etc.); 12 weeks
  - Antimetabolite therapy (*e.g.*, 5-fluorouracil); 8 weeks
  - Retinoids; 90 days
  - Liquid nitrogen, electrodesiccation, curettage; 60 days
  - Over-the-counter (OTC) wart therapies and cantharidin; 28 days

### 11.2. Concomitant Therapies

Concomitant therapies are any new or existing therapy received from Visit 1 until discharge from the study.

Concomitant therapies include drug (*e.g.*, prescription, over-the-counter [OTC]) and non-drug (*e.g.*, chiropractic, physical therapy, energy-based treatments) therapies. Subjects will refrain from receipt of any therapy in compliance with the inclusion/exclusion criteria. Subjects should refrain from changing the use of any concomitant therapies during the study.

All new or modified concomitant therapies used during the study must be recorded in the subject CRF.

### 11.3. Prohibited Therapies

During the course of this study, subjects are prohibited from using the following treatment therapies to treat the identified common warts:

- Intralosomal Therapy
  - Immunotherapy (e.g., *Candida* antigen, mumps antigen, *Trichophyton* antigen)
  - Anti-metabolite therapy (e.g., bleomycin, 5-fluorouracil);
- Systemic Therapy
  - Immunomodulatory/immunosuppressant therapy (e.g., etanercept, alefacept, infliximab);
  - Glucocortico-steroids (inhaled and intra-nasal steroids are permitted);
- Topical Therapy
  - LASER (e.g., pulsed-dye laser [PDL], light (e.g., intense pulsed light [IPL], photodynamic therapy [PDT], other energy-based therapy);
  - Immuno-therapy (e.g., imiquimod, squaric acid dibutyl ester [SADBE], etc.);
  - Anti-metabolite therapy (e.g., 5-fluorouracil);
  - Retinoids;
  - Liquid nitrogen, electrodesiccation, curettage;
  - Over-the-counter (OTC) wart therapies and cantharidin.

The investigator should notify the Medical Monitor immediately if any prohibited therapies are required to ensure subject safety.

Starting with Visit 2, subjects must not apply any topical products (e.g., moisturizers, sunscreens, etc.) to their identified common warts within **12 hours prior** to any study visit (Note: routine cleansing products are allowed).

After the completion of any study visit where a study medication treatment was performed subjects must **NOT wash/submerge** the treated common wart for at least **6 hours** and must not apply any topical products to the treated common wart for at least **6 hours**. Parents/legal guardians of children must ensure that the child does not put the treated area in their mouth, or eyes, until completely dry after the application. If the treated area is not completely dry 10 minutes after the application, the area should be blotted dry.

## **12. ASSESSMENTS OF CLINICAL EFFICACY**

### **12.1. Common Wart Identification**

At Visit 1, the investigator will identify at least one 1 and up to 6 common warts for treatment and evaluation.

At Visit 1, each identified common wart must:

- Have a longest axis that is  $\geq 3$  mm and  $\leq 8$  mm
- Have a thickness  $\leq 3$  mm
- Be a discrete lesion, i.e. each wart meeting the entry criteria must be clearly separated from other warts
- Be present for at least 4 weeks
- Not be a periungual, subungual, genital, anal, mosaic, plantar, flat or filiform wart
- Not be in an intertriginous fold
- Not be covered with hair which, in the Investigator's opinion, would interfere with the study medication treatments or the study evaluations

Not be in an area that may be occluded (*e.g.*, by clothing or footwear or in a skin fold).

Record the location of each identified common wart on the body charts in the CRFs indicating landmarks and distances to assist with confirming the location of the identified common wart at subsequent visits.

## **12.2. Standardized Photography**

At Visits 1, 2, 4, 6, 9-13 a qualified investigational center staff member will take standardized color photographs of each identified common wart.

Subjects at a sub-set of investigational sites (up to 3) will have additional standardized photographs taken of their each identified common wart at the following time-points:

- V2: 10 minutes post application
- V2: 1-hour post application
- V2: 24-hour post application

The photographs are to document the appearance and location of the each identified common wart. The subject's identity will not be revealed in the study photographs.

At Visit 2, the photographs must be taken prior to the study medication application.

Care must be taken to ensure the same lighting, background, subject positioning relative to the camera and camera settings are used for each photograph.

Sites will be provided with photography equipment and supplies necessary for obtaining the common wart photographs. Detailed instructions for obtaining and managing the photographs will be documented in the study specific Photography Manual and provided to the site at the study initiation visit.

### **12.3. Physician's Wart Assessment (PWA)**

The Physician's Wart Assessment (PWA) is the Investigator's assessment of the severity of each identified common wart at a particular time point. The Investigator should NOT refer to any other assessments to assist with this evaluation. This evaluation IS NOT a comparison with the PWA performed at any other visit.

At every study visit, the Investigator will assess each identified common wart and report the one integer that best describes the common wart severity using the following scale. At any visit where a study medication treatment is performed, the PWA must be completed prior to the treatment visit.

| Physician's Wart Assessment |   |
|------------------------------------|---|
| Grade                       | Descriptor   |
| 0                           | Clear: No visible wart. No further treatment is indicated                         |
| 1                           | Near Clear: a visible wart that is less than 3 mm in maximal diameter (or length) |
| 2                           | A visible wart $\geq$ 3 mm and $<$ 6 mm in maximal diameter (or length)           |
| 3                           | A visible wart $\geq$ 6 mm in maximal diameter (or length)                        |

The physician is encouraged to use a ruler or caliper and to feel the wart or skin area to help his/her assessment.

At Visit 1 for the subject to be enrolled and at Visit 2 for the subject to be randomized each identified wart must have a PWA grade  $\geq$  2.

At Visits 3-9, identified common warts must have a PWA  $> 0$  to be retreated. If the Investigator cannot assess the PWA for a common wart (e.g., the common wart cannot be visualized because of an LSR such as edema, scabbing, etc.) she/he must report the reason in the subject's CRFs. The identified common wart must not be retreated at that visit, and the subject should be seen at the next scheduled visit. All at home treatment visits will be based on the PWA score during the in-office visit.

Refer to [Appendix 2](#) for the PWA Site Manual.

### **12.4. Subject Instructions**

An investigational center staff member will dispense a Subject Instruction Sheet to each subject at Visit 1 (Refer to [Appendix 1](#)).

Throughout the study, the subjects should:

- Continue their routine cleansing regimen except they should avoid vigorous scrubbing of the identified common warts (e.g., loofah, back brushes, scrubbing straps, abrasive washcloths, sponges and cleansing pads, etc.)
- Continue their routine cosmetics and skin care products
- Avoid exposing the identified common warts to excessive natural or artificial ultraviolet radiation (e.g., sunlight, tanning beds) and use sunscreen on the common warts, if excessive exposure cannot be avoided
- Avoid activities that might irritate the common warts.
- Avoid the use of self-tanning lotions and spray tans near the common warts.
- Bring the subject instruction sheet and subject diary with them to each visit.
- Follow all instructions for the proper application of the A-101 study medication when applying product at home.

On study visit days, the subjects should:

- Wear loose fitting clothing to the visit (Note: clothing that comes in contact with the study medication may be bleached)
- Starting with Visit 2, not apply any topical products to the identified common wart within **12 hours** prior to the visit (Note: routine cleansing products are allowed)
- After the completion of any study visit where a study medication treatment was performed DO NOT:
  - Wash/submerge the treated common wart for at least **6 hours**
  - Apply any topical products to the treated common wart for at least **6 hours**.

**12.5.** Parents/legal guardians of children must ensure that the child does not put the treated area in their mouth, or eyes, until completely dry after the application. If the treated area is not completely dry 10 minutes after the application, the area should be blotted dry. **Other Study Supplies**

Aclaris Therapeutics, Inc. will provide:

- An appropriate ruler, or other instrument, for measuring of all common wart dimensions;
- Supplies and instructions for collecting, labeling, shipping and result reporting for the clinical laboratory tests from ACM Laboratories;
- Nitrile examination gloves
- Equipment, supplies and training for taking standardized photographs;

## **13. ASSESSMENT OF SAFETY**

In addition to reporting adverse events throughout the study the investigator, a designated and appropriately trained staff member or the subject, will perform the following safety assessments according to the schedules noted below.

### **13.1. Local Skin Reactions (LSRs)**

The LSR assessment is the Investigator's assessment of the signs and the subject's assessment of the symptoms associated with irritation at the identified common wart site (*i.e.*, the common wart and the skin immediately surrounding the common wart exposed to study medication). The Investigator may refer to previous photographs to assist with these assessments only AFTER the PWA has been performed.

The Local Skin Reaction signs to be assessed are:

- Erythema
- Edema
- Erosion
- Ulceration
- Vesicles/bullae
- Excoriations
- Scabbing

The Local Skin Reaction symptoms to be assessed (by the Subject) are:

- Stinging/burning
- Pruritus (itch)

At Visits 2-13, the Investigator will evaluate the LSR signs at the each identified common wart site as follows:

- At visits where a study medication treatment or retreatment is performed:
  - Perform an LSR assessment prior to any study medication applicationand

At Visits 2-13, the Subject will assess the LSR symptoms at the identified common wart site as follows:

- At visits where a study medication treatment or retreatment is performed:
  - Perform an LSR assessment prior to any study medication application

At visits where **NO** study medication treatment is performed:

Aclaris Therapeutics, Inc.

Protocol Number: A-101-WART-302

Amendment 3: Version 5 14 February 2019

- Perform an LSR assessment.

The Investigator and Subject should report the one integer that best describes the severity of each LSR sign or LSR symptom for the common wart site using the scale below:

| Local Skin Reactions |  |
|-----------------------------|--|
| Grade                | Descriptor  |
| 0                           | None; No signs or symptoms present.  |
| 1                           | Asymptomatic or mild symptoms; clinical or diagnostic observations only; intervention not indicated.                               |
| 2                           | Moderate; minimal, local or noninvasive intervention indicated.  |
| 3                           | Severe or medically significant but not immediately life threatening; disabling; limiting self-care of activities of daily living. |

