**Duration of Treatment**

The duration of the study participation is anticipated to be a maximum of 157 days per subject. The final visit (Visit 13) has a maximum allowable visit window of 7 days: Study visits are:

- Visit 1 (Day -13 to 0) screening
- Visit 2 (Day 1) randomization; study medication treatment
- Visit 3 (Day 8) study medication treatment
- Visit 4 (Day 15) study medication treatment
- Visit 5 (Day 22) study medication treatment
- Visit 6 (Day 29) study medication treatment
- Visit 7 (Day 36) study medication treatment
- Visit 8 (Day 43) study medication treatment
- Visit 9 (Day 50) study medication treatment
- Visit 10 (Day 60) follow up evaluations, no identified Wart retreatment
- Visit 11 (Day 78) follow up evaluations, no identified Wart retreatment
- Visit 12 (Day 106) follow up evaluations, no identified Wart retreatment
- Visit 13 (Day 137) follow up evaluations, no identified Wart retreatment; end of study

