A-101 ( $H_2O_2$ ) 45% (w/w) Topical Solution administered once weekly and twice weekly was well tolerated. Treatment emergent adverse events were predominantly mild and unrelated to study medication. Local Skin Reactions (LSRs) were predominantly mild and transient. The LSRs of pruritus and stinging reported by subjects, and crusting, edema, erythema, and scaling reported by the investigator following treatment generally resolved by Visit 13 (Day 134). There were no clinically significant changes during the study in laboratory evaluations or vital signs.

Aclaris Therapeutics, Inc.

Protocol Number: A-101-WART-302

Amendment 3: Version 5 14 February 2019

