The investigator and subject will assess each identified common wart for local skin reactions associated with irritation at Visits 2-13. At Visit 2-Visit 9, the investigator and subject will assess each identified common wart for LSRs prior to the application of the study medication. Refer to Section [13.1](#) for the complete list of Local Skin Reaction signs and symptoms.

During in-office visits, subjects 18 years of age and older will apply their A-101 study medication in the presence of the treating physician or a member of the investigational study staff that has been trained on the protocol. Subjects ages 1 to 17 will have their A-101 study medication applied by a parent/legal guardian in front of the treating physician or a member of the investigational study staff during in-office visits. If the identified common wart meets the criteria

for re-treatment as defined in Section 10.6 the lesion will be re-treated at Visits 3-9. Following application of study medication, subjects must NOT wash/submerge the treated wart for at least 6 hours and they must NOT apply any topical products to the treated common warts for at least 6 hours. Parents/legal guardians of children must ensure that the child does not put the treated area in their mouth, or eyes, until completely dry after the application. If the treated area is not completely dry 10 minutes after the application, the area should be blotted dry.All subjects will receive their second weekly treatment of the A-101 study medication at home on Days 4, 11, 18, 25, 25, 32, 39, 46, 53 as determined by the PWA assessment performed during the in-office visit. Subjects ages 1 to 17 will have their A-101 study medication applied by a parent or legal guardian. All subjects will need to document the application of A-101 study medication in a subject diary. The second weekly treatment will depend on the PWA performed during the in-office visit that week. If the identified common wart meets the criteria for re-treatment during the in-office visit, then the subject/parent/guardian will perform the second weekly treatment at home.

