### **14.2. Reporting Procedures**

#### **14.2.1. Procedures for Reporting Adverse Events**

At each post enrollment visit, the investigator or designee will question the subject to elicit AEs using a non-directive question such as “Has there been any change in your health since the previous study visit?”

The Investigator/designee will monitor the subject for at least 20 minutes after the Treatment Completion Time at any visit during which a study medication treatment is performed to elicit AEs in a similar manner.

If appropriate, based on the subject's response to non-directed questioning regarding AEs, the investigator or designee will follow-up with directed questions and appropriate evaluations.

Any AE noted during the reporting period must be reported in the source documents and on the appropriate AE CRF.

AEs that are defined as “Not Related” to the study medications will be followed until they are resolved or until the subject's last study visit. AEs that are defined as “Related” to the study medications will be followed until they are resolved or, if not resolved after the subject's last study visit, until in the opinion of the investigator, the AE reaches a clinically stable outcome with or without sequelae.

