### **3.3.3 Local Skin Reactions**

The number of subjects with local skin reaction signs that worsened by at least 1 grade from baseline any time after the first application of study medication will be tabulated according to treatment group for each sign as well any sign. A separate summary limited to LSRs that worsen and which occur within 30 days of the last application of study medication will be provided. The number of subjects with local skin reaction signs that worsened by at least 1 grade from baseline any time after the first application of study medication will be tabulated by treatment group and Fitzpatrick Skin Type for each sign as well as any sign.

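### The LSR scale is never scheduled after an application, so reactions that resolve before the next visit are captured only unsystematically

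*Protocol*

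**What the plan says.** Protocol 13.1 lists seven signs graded by the investigator and two symptoms (stinging/burning and itch) graded by the subject, each from 0 to 3. For visits with treatment it gives one time point: "Perform an LSR assessment prior to any study medication application". Footnote 13 of Protocol Table 2 agrees that at Visits 2-9 "the investigator and subject will assess each identified common wart for LSRs prior to the application of the study medication", and the SAP's schedule repeats this. Visit 2 is therefore a pre-dose baseline. Section 13.1 also requires a grading "At visits where NO study medication treatment is performed", which covers Visits 10-13.

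Other passages deal with the period after dosing without using the scale. Protocol 14.2.1 says that staff "will monitor the subject for at least 20 minutes after the Treatment Completion Time" in order to elicit adverse events (AEs). Protocol 10.7 has a contingency rule: "If severe erythema and edema develop, then the treatment cycle should be discontinued for that specific treatment application". On earlier experience, Protocol 5.2 reports that "Local Skin Reactions (LSRs) were predominantly mild and transient".

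SAP 3.3.3 counts subjects whose LSR signs "worsened by at least 1 grade from baseline any time after the first application of study medication".

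**The concern.** The product is a 45% hydrogen peroxide solution, and the LSR scale is the only instrument in the plan that grades local irritation per wart and per sign. If a reaction appears soon after an application and settles within a day or so, the scheduled gradings cannot see it. The SAP table is worded as if it covered the whole period from the first dose onward. Its data can show only what persists to the next visit, and a reader of the study report could take it for the overall incidence of local reactions.

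The subject-rated symptoms have a further gap. Section 13.1 gives no recall period, and grade 0 is worded in the present tense, so stinging that has passed need not be reported at the next visit. SAP 3.3.3 then tabulates signs only. Protocol 15.4, by contrast, says that LSR scores will be tabulated without limiting them to signs.

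At stake is the description of local tolerability. The efficacy analyses are not affected.

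**Working it through.** The documents state no interval between application and LSR grading, so there is no figure to reproduce. The intervals follow from the schedule.

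**Inputs**
- In-office applications: Days 1, 8, 15, 22, 29, 36, 43 and 50 (Protocol synopsis, for example "Visit 3 (Day 8) study medication treatment"). The window at Visits 3-9 is ±1 day (Table 2).
- Home applications: Days 4, 11, 18, 25, 32, 39, 46 and 53, with a window of +1 day (Table 2).
- Visit 10: Day 60, with a window of +4 days (Table 2).

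**Formulas**
- Shortest gap = earliest allowed visit day − latest allowed day of the previous application.
- Longest gap = latest allowed visit day − earliest allowed day of the previous application.

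**Results**

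| Grading at | Since | Nominal (days) | Shortest | Longest |
|---|---|---|---|---|
| Visits 3-9 (Visit 3 shown) | home dose | 8 − 4 = 4 | 7 − 5 = 2 | 9 − 4 = 5 |
| Visit 3 | in-office dose | 8 − 1 = 7 | 7 − 1 = 6 | 9 − 1 = 8 |
| Visits 4-9 (Visit 4 shown) | in-office dose | 15 − 8 = 7 | 14 − 9 = 5 | 16 − 7 = 9 |
| Visit 10 | last home dose | 60 − 53 = 7 | 60 − 54 = 6 | 64 − 53 = 11 |

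Both schedules advance by 7 days, so the home-dose row is the same at each of Visits 3-9. It applies only when the home dose was given; in a week without one, the in-office rows apply. Visits 11, 12 and 13 fall nominally 78 − 53 = 25, 106 − 53 = 53 and 137 − 53 = 84 days after the last home dose.

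**Reading the table.** The shortest gap after any application is 2 days, so 0 of up to 16 applications has an LSR grade later that day or on the next day. For home doses before Visits 3-9, a reaction that clears in less than 2 days is missed whatever the windows, and one that lasts beyond 5 days is present at the next grading. Between those limits, capture depends on when the subject attends. A reaction to an in-office dose must last at least 5 days to be present at the next grading, by which time a home dose has usually intervened.

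**Other records of the acute phase**
- The 20-minute observation (14.2.1) starts with a non-directive question. It applies to in-office doses only, 8 of 16.
- Post-application photographs are taken at 10 minutes, 1 hour and 24 hours, after the Visit 2 dose only. That is 1 of 16 applications, at up to 3 of about 25 sites (3/25 = 12%), with no grade attached (12.2).
- The home instruction sheet (Appendix 1) asks for a diary record of how many times the wart was treated. It does not ask for a reaction grade.

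**The case against.** The case for leaving the schedule alone has real content.

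- **Acute reactions are not invisible.** A reaction reported as an AE is rated mild, moderate or severe (14.1.4). After the opening question, staff may follow up with directed questions and evaluations (14.2.1). Severe erythema and edema end the application cycle, and SAP 3.3.1 reports the share of treatments completed in 1, 2 or 3 applications, which is an indirect signal. Severe irritation on a home treatment day must be notified to the site (10.5), and refusals are recorded with reasons (10.8).
- **Pre-dose grading has a purpose.** It feeds the retreatment criteria in 10.5.
- **Transient has no stated length.** Section 5.2 continues that the listed reactions had generally resolved by Visit 13 (Day 134). Nothing in the documents says hours rather than weeks, and the rule in 10.7 is conditional, not a forecast.
- **Safety summaries are descriptive.** Protocol 15.4 plans no inferential testing.

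Most of this stands, and it limits what can be concluded. A reader might infer that acute reactions are never graded; that holds for the LSR scale alone. A reader might also infer that LSRs are graded only before dosing, but Visits 10-13 are graded with no dosing. The most tempting inference is that reaction rates will be understated mainly in the active arm, making A-101 look better tolerated than it is. With no time course in the documents, neither the size nor the direction can be derived. Nor does SAP 3.3.3 understate stinging/burning: that symptom is absent from its table.

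The objection does not show that the gap is filled. Non-directive questioning, cycle counts and a small photographic subset do not amount to systematic grading per wart and per sign, and the first is a weak instrument in subjects as young as 1 year. Protocol 14.1.1 also restricts AE reporting of worsening in wart assessments to cases where medication is interrupted or stopped or therapy is needed. If a site reads that as including LSRs, self-limiting reactions could drop out of the AE data too.

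**Conclusion.** The point holds in limited form. The LSR scale is never scheduled after an application. It is applied 2 to 5 days (nominally 4) after the last home dose at Visits 3-9, and 6 to 11 days (nominally 7) after the last dose at Visit 10. Reactions that resolve sooner are recorded only if they surface through an unsystematic route, and the wording of SAP 3.3.3 claims more than its data can show.

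The intervals assume that visits and home doses stay within their windows and that the home dose was given. The consequence depends on how long reactions last, which the documents do not say, so no size and no difference between arms is claimed. This is a worthwhile, inexpensive improvement to safety description. It does not threaten the primary conclusion.

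**What to change.** **Protocol 13.1 and Table 2 footnote 13.** At each of Visits 2-9 where treatment is given, add one LSR grading at the end of the existing 20-minute observation. The subject rates stinging/burning and itch. A trained staff member already present grades the signs, where possible someone other than the PWA rater; the opening of Section 13 allows designated staff to make safety assessments. Withhold these grades from the PWA rater. Section 12.3 has the PWA completed before treatment, so that day's PWA is unaffected and only later ones need protecting.

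**SAP 3.3.3.** Tabulate post-application LSRs separately from pre-application and follow-up LSRs, include both symptoms as well as the signs, and label the existing table as pre-application/follow-up gradings. SAP 3.6 mentions a correction made after unblinding. If data collection is over, the labelling, the symptom table and a stated limitation are still possible.

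**Cost.** The new grading has 7 + 2 = 9 items per treated wart. With 6 warts that is at most 9 × 6 = 54 grades per visit and 54 × 8 = 432 over eight visits. Reported LSR rates will probably rise. The person supervising an application may be the treating physician, so separating the raters may need extra staff, and signs graded by a different person are less comparable with the investigator's baseline. Coverage stays partial: 8 of 16 applications, and only about the first 20 minutes after each. The period from then to the next visit, and all home doses, remain ungraded.
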